7.1.3.1 Delay of Study Vaccination

If any of these events occur at the time scheduled for vaccination, the subject may be vaccinated at a later date.

- Acute moderate or severe infection with or without fever at the time of vaccination.
- Fever, defined as oral temperature $\geq 38.0^{\circ}\text{C}$ (100.4°F) at the time of vaccination.

Subjects with a minor illness without fever, as assessed by the participating site PI or appropriate sub-investigator, can be administered vaccines. Subjects with an oral temperature of 38.0°C (100.4°F) or higher will be re-contacted within the window specified in the SOA and re-evaluated for eligibility.

It is preferred that the vaccination still occur within the window specified in the SOA if possible but delays outside the windows are permitted (would still be a protocol deviation).

7.1.4 Follow-up for Subjects that Discontinued Study Intervention

Discontinuation of study intervention does not require discontinuation from the study, and the remaining study procedures should be completed as indicated by the SOA. If a clinically significant finding is identified, including, but not limited to, changes from baseline, after enrollment, the participating site PI or qualified designee will determine if any change in subject management is needed. Any new clinically relevant finding will be reported as an AE.

7.2 Subject Withdrawal from the Study and Replacement

Subjects are free to withdraw from participation in the study at any time upon request, without any consequence.

A study subject will be discontinued from participation in the study if any of the following reasons occur prior to initial dosing:

- Request by the subject to terminate participation.

- Initial vaccine is not administered.

A subject may be removed from the study for the following reasons post initial dosing; however, whenever possible the subject should be followed for safety and immunogenicity evaluations per protocol:

- Subject becomes pregnant before receiving the second or third dose of vaccine.
- Study non-compliance to protocol requirements that in the opinion of the participating site PI or appropriate sub-investigator poses an increased risk or compromises the validity of the data.
- Lost to follow-up.
- If the subject met an exclusion criterion for participation in the study (either newly developed or not previously recognized) that precludes further study participation.
- Request of primary care provider, the IRB, FDA, or NIAID.
- Medical disease or condition, or new clinical finding(s) for which continued participation, in the opinion of the participating site PI or appropriate sub-investigator might compromise the safety of the subject, interferes with the subject's successful completion of this study, or interferes with the evaluation of responses.
- If any AE or situation occurs such that continued participation in the study would not be in the best interest of the subject.
- Any SAE judged to be related to vaccine.

If the subject agrees, every attempt will be made to follow all AEs through resolution or stabilization.

Subjects who withdraw, or are withdrawn from this study, or are lost to follow-up after signing the informed consent form (ICF) and administration of the study product will not be replaced.

Subjects who withdraw, or are withdrawn from this study, or are lost to follow-up after signing the ICF but before administration of the study product may be replaced.

The reason for subject discontinuation or withdrawal from the study will be recorded on the appropriate DCF.

7.3 Lost to Follow-Up

A subject will be considered lost to follow-up if he or she fails to appear for a follow-up assessment. Extensive effort (i.e., generally three documented contact attempts via telephone calls, e-mail, etc., made on separate occasions) will be made to locate or recall the subject, or at least to determine the subject's health status. These efforts will be documented in the subject's study file.

8 STUDY ASSESSMENTS AND PROCEDURES

8.1 Screening and Immunogenicity Assessments

8.1.1 Screening or Enrollment/Baseline Procedures

There is a small amount of risk to subjects who report that they are in good health but have an unknown health problem at the time of the enrollment/baseline visit. Screening assessments can occur up to 28 days before or at the subject's first vaccination visit (Day 1). At the screening (optional) or enrollment/baseline visit, and prior to any other study-related activities, the participating site PI or appropriate sub-investigator will provide the subject with detailed study information and will obtain written informed consent.

Some or all of the following assessments are performed during the screening (optional) or enrollment/baseline visit to determine eligibility requirements as specified in the inclusion and exclusion criteria:

- Obtain medical history.
- Review pre-study medications and therapies at screening and record on the appropriate DCF. Review of adult vaccinations, including any other SARS-CoV-2 or other experimental coronavirus vaccines.
- Review any participation in investigational trials in the last 6 months.
- Measure vital signs (HR, BP, and oral temperature), and height and weight for determination of BMI.
- Targeted physical examination based upon symptoms elicited in the medical history
- Review of birth control history with female subjects of childbearing potential.
- Counsel subjects to use adequate birth control methods required during the trial to avoid pregnancy.
- Urine pregnancy test (in women of childbearing potential). If urine pregnancy is done at separate screening visit, repeat urine pregnancy test will be done within 24 hours of study vaccine administration.
- Review inclusion and exclusion criteria.

The screening process can be suspended prior to complete assessment at any time if exclusions are identified by the study team.

Study subjects who qualify for inclusion will be contacted and scheduled for enrollment and first vaccination within the window for enrollment unless the screening and vaccination are scheduled on the same day.

If a physiologic parameter, e.g., vital signs, is outside of the protocol-specified range, then the measurement may be repeated once if, in the judgment of the participating site PI or appropriate sub-investigator, the abnormality is the result of an acute, short-term, rapidly reversible condition (e.g., stress, anxiety or "white coat syndrome") or other source of error. A physiologic parameter

may also be repeated if there is a technical problem with the measurement caused by malfunctioning, or an inappropriate measuring device (i.e., inappropriate-sized BP cuff).

A subject may be re-screened if there is a transient disease status (e.g., subject complained of a “cold or fever” and met a temporary delaying enrollment criterion of acute illness or fever), or if a protocol eligibility criterion that is not met at the initial time of screening, will be met by rescreening at a later date (e.g., a medication taken within exclusionary window at the time of first screening that would not be within exclusionary window at a later rescreen).

No subjects may be screened more than twice due to a screening failure result as defined above.

Subjects will be provided the results of abnormal clinical findings necessitating follow-up at the discretion of the participating site PI or appropriate sub-investigator. Research laboratory results will not be provided to the subject.

The screening and first vaccination procedures both can be conducted at the enrollment/baseline visit.

8.1.2 Immunogenicity Evaluations

Serological Immunogenicity Assays:

The following serological immunogenicity assays may be performed:

- IgG ELISA to SARS-CoV-2 proteins.
- Neutralization assays using different strains of SARS-CoV-2 pseudovirus.
- Neutralization assay using different strains of live SARS-CoV-2.
- Quadriplex MSD assay (Nucleocapsid protein, Receptor binding domain, spike protein and variant spike protein)

Preparation of blood samples and shipping instructions for serological immunogenicity assays are outlined in the protocol-specific MOP. Inability (e.g., failure of venipuncture) to collect all baseline samples on Day 1 will not exclude the subject from further participation in this study as long as a minimum of baseline serum for serological immunogenicity assays is collected.

Cellular Immunology Assays:

This trial may also investigate B and T cell immune responses using multiparametric flow cytometry.

Refer to the protocol-specific immune monitoring plan for details.

Preparation of blood samples and shipping instructions for cellular immunology assays are outlined in the protocol-specific MOP.

The volume of venous blood to be collected for immunogenicity evaluations is presented in Table 10, Table 11, and Table 12.

Mucosal Antibody Assays:

Salivary and nasal mucosal samples collected from cohort 2 study participants will be evaluated for total and virus-specific IgG and IgA immune responses using MSD assay. Mucosal antibody

presence and magnitude will be correlated with serologic results. Preparation of the salivary and nasal samples and shipping instructions for immunogenicity assays are outlined in the protocol-specific MOP.

8.1.3 Samples for Illness Visit

In the event that a subject develops symptoms compatible with COVID-19, the site will follow with an unscheduled Illness Visit. If a volunteer is asymptomatic but tests positive for COVID-19, the site may follow-up with a study visit on an optional basis, as staff availability and resources allow. Wide discretion is given to sites for the assessment of COVID-19 illness. Guidance can be found at the CDC website (2020 Interim Case Definition):

<https://wwwn.cdc.gov/nndss/conditions/coronavirus-disease-2019-covid-19/case-definition/2020/#:~:text=Clinical%20Criteria,of%20breath%2C%20or%20difficulty%20breathin>
g

The following intervention will be performed in the event of an illness visit:

Nasal or nasopharyngeal (NP) swabs for PCR and sequencing

Two nasal or NP swabs will be obtained for the purposes of 1) conducting qualitative analysis to assess for the presence of SARS-CoV-2 virus, and 2) conducting PCR quantitation/sequencing in the event that nasal or NP swab #1 is positive for SARS-CoV-2.

The first nasal or NP swab will be processed at the local level with results informing the disposition of the second nasal or NP swab. The sites will freeze and store the second swab (refer to MOP for labeling, storage, and shipping instructions) for potential shipment to the central repository for processing.

8.1.4 Samples for Genetic/Genomic Analysis

8.1.4.1 Genetic/Genomic Analysis

DNA obtained from B-cells may be sequenced to identify B cell receptors and monoclonal antibodies. The DNA data may be used to synthesize antigen-specific antibodies to characterize antibody binding. Secondary research samples may also be used for other genomic analysis, including, but not limited to, single nucleotide polymorphisms (SNP) arrays, human leukocyte antigen (HLA) typing, transcriptomic analysis, evaluation of the immune response to the vaccine, and/or evaluation of any AE from the vaccine.

8.1.4.2 Genetic Privacy and Confidentiality

Any genetic data generated will be kept private. Informed consent permitting data sharing will be part of the consent process. Subjects will be informed that the evolution of genomic technology and analytical methods raises the risk of re-identification, even when specimens are de-identified. No data that may identify specific subjects will be kept with the genetic data.

8.1.4.3 Management of Results

All genetic testing in this protocol will be performed for research purposes only and is not performed in a Clinical Laboratory Improvement Amendments (CLIA) certified laboratory. Therefore, results will not be shared with the subjects.

8.2 Safety and Other Assessments

Study procedures are specified in the SOA. A study clinician, licensed to make medical diagnoses and listed on the Form FDA 1572 as the participating site PI or appropriate sub-investigator, will be responsible for all study-related medical decisions.

Medical history:

A complete medical history will be obtained by interview of subjects at the screening (optional) or enrollment/baseline visit. Subjects will be queried regarding a history of significant medical disorders.

At all subsequent visits an interim medical history will be obtained by interview of subjects and any changes since the previous clinic visit or telephone call will be noted. The interim medical history should include an assessment to identify intercurrent Protocol Specified AESIs, MAAEs, and NOCMCs.

Physical examination:

A symptom-directed (targeted) physical examination will be performed if indicated at any timepoint at the discretion of the participating site PI or appropriate sub-investigator, if necessary, to evaluate AEs.

Reactogenicity assessments of solicited AEs, occurring from the time of each vaccination through 7 days post vaccination, will include an assessment of injection site reactions—erythema, edema/induration and pain, as well as systemic reactions—fever, fatigue, chills, myalgia (exclusive of the injection site), arthralgia, headache, and nausea. Pre-administration reactogenicity assessments will be performed immediately prior to each vaccination to establish baseline, then the vaccination will be given.

Subjects will be observed in the clinic for at least 30 minutes post each vaccination. The vaccination site will be examined, post-administration reactogenicity assessments will be performed, and any AEs/SAEs will be recorded on the appropriate DCF prior to discharge from the clinic. The vaccination site will also be examined 7 days after vaccination.

Vital signs: Vital sign measurements will include systolic and diastolic BP, HR, and oral temperature. Vital signs will be measured at timepoints specified in the SOA. On vaccination days, vital sign measurements will be collected prior to vaccine administration. Vital signs assessed on Day 1 prior to the first vaccination will be considered as baseline. Subjects must not eat or drink anything hot or cold within 10 minutes prior to taking oral temperature.

Urine pregnancy test: Urine pregnancy test will be performed locally by the site laboratory within 24 hours prior to each vaccination, and as needed at interim or

unscheduled visits for all women of childbearing potential. Results must be confirmed as negative prior to enrollment on Day 1 and administration of each vaccination as applicable.

Memory aid:

All subjects will complete a Memory Aid from the time of each vaccination through 7 days post each vaccination. Memory Aids will be reviewed with the subjects for any AEs (solicited injection site and systemic reactions, as well as unsolicited AEs), SAEs and concomitant medications during telephone calls 7 days after each vaccination. Based on the information collected, subjects may be asked to return to the clinic for evaluation. Memory Aids will be reviewed again, and subjects will be assessed for delayed onset local reactions 14 days after booster vaccination (initial vaccination in Cohort 1, delayed vaccination in Cohort 2). Memory aids will be reviewed 7 days after each vaccination in Cohort 2.

Table 10: Venipuncture Volumes for Cohort 1 (One Vaccination – EUA Dosed Cohort)

Study Day	-28 to -1	1	8	15	29	91	181	273	366	Early Termination Visit	Total Volume of Blood Drawn (mL)
Visit Window (\pm number of days)		0	1	2	2	7	14	28	28		
Study Visit	Screening (optional) 00	01	02	03	04	05	06	07	08		
Vaccination		X									
Serum for Serological Immunogenicity Assays ¹		16		16	16	16	16	16	16	16 ²	96
PBMCs (and Plasma) for Cellular Immunology Assays		64		64			64		64	64 ²	256
Serum for Secondary Research		16		16	16	16	16	16	16	16 ²	96
Per Visit Blood Volume Total (mL)		96		96	32	32	96	32	96	96 ²	448
Cumulative Blood Volume (mL) (prior 56 days)		96	96	192	224	32	96	32	96		
Running Blood Volume Total (mL)		96	96	192	224	256	352	384	480		

¹ Inability (e.g., failure of venipuncture) to collect all baseline samples on Day 1 will not exclude the subject from further participation in this study as long as a minimum of baseline blood volume is collected. Refer to the Blood Collection Summary Table in the MOP for the minimum number of expected aliquots for this blood draw volume and minimum aliquots required to completed testing under the protocol

² These blood volumes are not included in the blood volume totals.

Table 11: Venipuncture Volumes for Cohort 2: (Up to Three Vaccinations)

Study Day	-28 to -1	1	8	29	36	43	Delayed Boost to occur \wedge Day 181 (window +/- 30 days) from Dose	1B	8B	15B	29B	91B	181B	366B	Early Termination Visit	Total Volume of Blood Drawn (mL)
Visit Window (\pm number of days)		0	1	2	3	3		0	1	2	2	7	14	28		
Study Visit	Screening (optional) 00	01	02	3	04 ³	05 ³		06 ³	07 ³	08 ⁴	09 ⁴	10 ⁴	11 ⁴	12 ⁴		
Vaccination		X		X				X								
Serum for Serological Immunogenicity Assays ¹		16		16		16		16		16	16	16	16	16	16 ²	144
PBMCs (and Plasma) for Cellular Immunology Assays		64		64		64		64		64	64	64	64	64	64 ²	512
Serum for Secondary Research		16		16		16		16		16	16	16	16	16	16 ²	144
Per Visit Blood Volume Total (mL)		96		96		96		96		96	32	96	96	96	96 ²	800
Cumulative Blood Volume (mL) (prior 56 days)		96	96	192	192	288	96	96	192	224	96	96	96			
Running Blood Volume Total (mL)		96	96	192	192	288	384	384	480	512	608	704	800			

¹ Inability (e.g., failure of venipuncture) to collect all baseline samples on Day 1 will not exclude the subject from further participation in this study as long as a minimum of baseline blood volume is collected. Refer to the Blood Collection Summary Table in the MOP for the minimum number of expected aliquots for this blood draw volume and minimum aliquots required to completed testing under the protocol

² These blood volumes are not included in the blood volume totals.

³ Visits 05-07 windows should be based off the actual Visit 03 date.

⁴ Visits 08-12 windows should be based off the actual Visit 06 date.

Table 12: Venipuncture Volumes for Cohort 2: (Fourth Vaccination)

Study Day		1C	8C	15C	29C	91C	181C	Illness/ Unscheduled Visit	Early Termination Visit
Visit Number	Boost to occur \geq 120 days \leq 366 days from Dose 3	13	14	15	16	17	18		
Window (+/-)		0 ¹	1 ²	2 ²	2 ²	7 ²	14 ²		
Immunoassays									
Serum- Humoral Assays		32		32	32	32	32		32 ³
PBMC Cellular Assays & plasma		64		64			64		64 ³
Daily Volume (mL)		96		96	32	32	96		96 ³
Cumulative Volume (mL)		96		192	224	256	352		
Running Blood Volume Total (mL) ⁴		800		896	928	960	1056		

¹ Visits 13 windows should be based off the actual Visit 06 date.

² Visits 14-18 windows should be based off the actual Visit 13 date.

³ These blood volumes are not included in the blood volume totals.

⁴ Running blood volume continues after visit 11 for those receiving a 2nd booster in cohort 2 (will occur prior to originally planned visit 12). For subjects who are boosted after visit 10, the running blood volume will be 96 mL less.

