SAEs, Protocol specified AESIs, MAAEs, and NOCMCs			X	X	X	X		X	X	X	X	X	X	X	X	X
Nasal or NP swab for PCR & Sequencing															X ^h	
Immunoassays																
Serum- Humoral Assays		32		32		32		32		32	32	32	32	32		32
PBMC Cellular Assays & plasma		64*		64*		64*	64		64	64	64	64	64		64	
Daily Volume (mL)		96		96		96	96		96	32	96	96	96		96	
Cumulative Volume (mL)		96		192		192	384		480	512	608	704	800			

^a Optional screening visit – informed consent and height/weight only performed at screening or Day 1

^b Telephone visit

^c EUA-dosing with 28-day interval – new constructs may be added as EUA is awarded and vaccine available

^d Delayed booster dose will be the 50 mcg dose of Moderna mRNA-1273. It will be administered on study day 1B which is 181 days with a window of +28 days after the second vaccine dose. If no booster administered; safety visits will continue as per [Table 6](#). If Covid-19 infection is detected in the interval between the primary series and the estimated time of booster administration, volunteers may remain in the study (with a minimum 28 day interval between infection and boost)

^e Vital signs before and after vaccination. Otherwise, only as clinically indicated.

^f For women of childbearing potential, a negative urine pregnancy test on Days 1 and 1B (delayed boost) will be performed with negative results confirmed prior to each dosing

^g Review 7-day Memory Aid data for delayed booster dose.

^h Collect nasal or NP swabs (x 2) for PCR. Sequencing will be performed on all illness visit-confirmed SARS-CoV-2 specimens.

*Collection of PBMC for cellular assays is performed at the discretion of the site, based on the capacity for PBMC processing

Table 5: SOA for Prospective Cohort 2 (2nd booster dose)

Study Day		1C	8C ^b	15C	29C	91C	181C	Illness/Unsch Visit	Early Term Visit
Visit Number		13	14	15	16	17	18		
Window (+/-)		0	1	2	2	7	14		
Informed Consent		X							
Eligibility Criteria		X							
Vaccination		X ^a							
Concomitant Meds		X	X	X	X				
Interim History		X	X	X	X	X	X	X	X
Physical Exam - Targeted		X		X	X	X	X	X	X
Vital Signs ^c		X		X	X			X	
Saliva Mucosal Sample		X		X	X	X	X		X
Nasal Mucosal Sample		X		X	X	X	X		X
Urine β-HCG ^d		X							
Memory Aid, Solicited AEs	Boost to occur ≥ 120 days and ≤ 366 days from Dose 3	X	X	X ^e					
Unsolicited AEs		X	X	X	X				
SAEs, Protocol specified AESIs, MAAEs, and NOCMCs		X	X	X	X	X	X	X	X
Nasal or NP swab for PCR & Sequencing								X ^f	
Immunoassays									

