infection. They will be assigned to receive COVID-19 vaccine under EUA dosing (as programmatically outlined in Table 9. Additional pools of subjects can be included if needed as additional COVID-19 vaccines are awarded EUA. These pools of participants were to be assigned a novel homologous or heterologous variant boost or heterologous platform boost at a minimum of 12 weeks following receipt of EUA dosing and followed through 12 months after the last vaccination. As booster vaccines have been approved for individuals at an interval of 6 months from the primary series, under EUA, all Cohort 2 volunteers will be offered a booster of mRNA-1273 at the approved 50 mcg dose at Day 181 (+/- 30 days following dose 2 of their primary series. A telephone visit will occur one week after each primary EUA vaccination and one week after the booster dose. In person follow-up visits will occur on 14 days following completion of EUA vaccinations and on days 14, and 28 days after the booster dose, as well as 3, 6, and 12 months post the booster vaccination. A fourth dose of COVID-19 vaccine will be administered to participants using the Moderna mRNA-1273.222 bivalent vaccine at an interval of 4 to 12 months after the third dose (1st booster). In addition to the other immunologic assays planned for earlier parts of the study (including innate, cellular and humoral responses), samples also will be collected to measure mucosal immune responses before the booster dose and on days 14 and 28, and at 3 months and 6 months after the fourth dose (2nd booster). Due to the surge of the Omicron variant and breakthrough infections, volunteers who contract symptomatic or asymptomatic COVID-19 between completion of their EUA primary series and the scheduled booster dose will be allowed to continue in the study. The interval between the COVID-19 infection and booster dosing should be a minimum of 28 days.

Table 9: Cohort 2 Treatment Arms

Group	Sample Size	First Vaccination	Second Vaccination		Booster Vaccination 1		Booster Vaccination 2	
		Product and Dose	Interval	Product and Dose	Interval	Product and Dose	Interval	Product and Dose
1	250	100 mcg mRNA-1273	28 days	100 mcg mRNA-1273	~6 months	50 mcg mRNA-1273	4-12 months	50 mcg mRNA-1273.222

For both Cohorts 1 and 2, reactogenicity will be assessed at the above-mentioned visits and blood will be drawn for immunogenicity assays at the in-person follow-up visits.

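### Protocol Table 11 ties the Day 8B call after the first Cohort 2 booster to the Dose 2 date, contradicting the text that places the call one week after the booster

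*Protocol*

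**What the plan says.** Protocol Table 11 (Section 8.2) gives the blood volumes and visit windows for Cohort 2 up to the first booster. Dose 2 is Visit 03 (Day 29). The booster phase runs "1B 8B 15B 29B 91B 181B 366B", numbered Visits 06 to 12. Visit 06 is therefore the booster and Visit 07 is Day 8B, with a window of ±1 day. Table 4 in Section 1.2 has the same mapping and marks Visit 07 as a telephone visit.

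Two footnotes to Table 11 set the anchors:

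- Footnote 3, marked on Visits 04 to 07: "Visits 05-07 windows should be based off the actual Visit 03 date".
- Footnote 4, marked on Visits 08 to 12: "Visits 08-12 windows should be based off the actual Visit 06 date".

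The body text times the call differently. Section 4.1: "A telephone visit will occur one week after each primary EUA vaccination and one week after the booster dose". Section 8.2 has the Memory Aid reviewed "during telephone calls 7 days after each vaccination". For the second booster, Table 12 says: "Visits 14-18 windows should be based off the actual Visit 13 date". Visit 13 is that booster and Visit 14 is the matching Day 8C call.

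The interval from Dose 2 to the first booster is itself stated in more than one way. Section 4.1 puts it "at Day 181 (+/- 30 days following dose 2 of their primary series". Note d to Table 4 says "which is 181 days with a window of +28 days after the second vaccine dose". The Table 4 column header sets a minimum of 181 days but also gives a ±30-day window.

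**The concern.** A call meant to follow the booster has its window counted from a vaccination about six months earlier. If the booster moves within its permitted window, the body text moves the call with it and footnote 3 does not. The booster has documented reasons to move: a minimum of 28 days must separate an infection from boosting, and Section 7.1.3.1 permits delays for acute illness or fever.

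The call is the first scheduled contact after observation on the booster day. It is also the first of two reviews of the Memory Aid, which supplies a primary endpoint: solicited adverse events for 7 days after the boost. On most permitted booster days a site cannot satisfy both instructions. It either calls at the wrong time or calls on time and logs a deviation that is not real.

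Footnote 3 has a second defect. Its marker is on Visit 04 (Day 36, the call after Dose 2), but its text starts at Visit 05, so Table 11 leaves Visit 04 without a stated anchor.

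**Working it through.** **Inputs**

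- Visit 07 follows Visit 06 by 8 − 1 = 7 days, ±1 (Tables 4 and 11).
- Nominal booster day: Dose 2 + 181 (Section 4.1; Table 4 note d).
- Permitted booster days, counted from Dose 2: 151 to 211 under ±30 (Section 4.1), which is 61 days; 181 to 209 under +28 (Table 4 note d), 29 days; 181 to 211 if the Table 4 header is read as at least 181 and up to +30, 31 days.

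**Assumption.** No document states a day for 8B counted from Dose 2. I take a Visit 03 anchor to mean 181 + 7 = 188 days after Dose 2, so the footnote 3 window is days 187 to 189. Counting a literal 7 days from Visit 03 gives study Day 29 + 7 = 36, which is already Visit 04, so that reading cannot be meant.

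**Comparison.** For a booster on day b, the body text puts the call in b + 6 to b + 8. This shares at least one day with 187–189 when |(b + 7) − 188| ≤ 2, that is, b = 179 to 183. A call exactly 7 days after the booster is inside the footnote 3 window when |(b + 7) − 188| ≤ 1, that is, b = 180 to 182. The whole footnote 3 window precedes the booster when b ≥ 190.

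| Booster window | Windows overlap | Exact 7-day call in window | Call window wholly before booster |
|---|---|---|---|
| 151–211 | 5/61 (8%) | 3/61 (5%) | 22/61 (36%) |
| 181–209 | 3/29 (10%) | 2/29 (7%) | 20/29 (69%) |
| 181–211 | 3/31 (10%) | 2/31 (6%) | 22/31 (71%) |

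Under ±30, the Dose 2-based target runs from 188 − 151 = 37 days after the booster to 211 − 188 = 23 days before it.

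**Check of the alternative.** Anchored to the actual Visit 06 date, the call falls 6 to 8 days after the booster for every booster date. That agrees with Sections 4.1 and 8.2 and with the Table 12 rule.

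**Likely origin.** If footnote 3 should cover Visits 04–06 and footnote 4 Visits 07–12, one slip of a visit number explains both the Visit 07 anchor and the Visit 04 omission. This is an inference.

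**The case against.** The strongest reply is that the intended timing is plain. The label 8B, Section 4.1 and Section 8.2 all point to one week after the booster. Section 8.2 refers study procedures to the schedule of activities, and the schedule in Table 4 gives no Visit 03 anchor for this visit. The conflicting rule is a footnote in a blood-volume table, on a visit with no blood draw. Many sites would probably call on time, and no site is likely to attempt a post-booster call before the booster. This stands, and it limits the practical effect. It does not remove the conflict, because Table 11 is the only place in the supplied documents that names an anchor for Visit 07.

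A reader might infer that Section 9.3 would drop these participants' data as substantially out of window. The documents do not support that. The per-protocol set is carved from the mITT set, which is defined by blood samples, and it serves immunogenicity. Solicited events are analysed in the safety population, which has no visit-window exclusion.

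A reader might also infer that reactogenicity data or a halting event would be lost. That is not shown either. Participants complete the Memory Aid through day 7, and it is reviewed again at Day 15B (Visit 08), which footnote 4 correctly anchors to the booster. Spontaneously reported events are recorded, unscheduled visits exist, and serious events must be reported within 24 hours of site awareness.

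Finally, the percentages depend on the Dose 2 + 188 assumption and on which booster window is used. This is also correct. The finding that the windows rarely overlap holds under each stated booster window.

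**Conclusion.** Footnote 3 is wrong as written for Visit 07. It contradicts Sections 4.1 and 8.2 and departs from the Table 12 rule for the second booster. Under the Dose 2 + 188 (±1) assumption, the two call windows overlap on about 8% to 10% of permitted booster days. That is a share of calendar days. It would be a share of participants only if booster dates were spread evenly, which the documents do not show, so it should not be read as most participants being out of window.

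The consequence is a mistimed first post-booster safety and Memory Aid contact, or false deviation entries, for Cohort 2 participants (about 250 planned) who receive the first booster. Whether false entries actually arise depends on the electronic data capture settings and the manual of procedures, which were not supplied. The supplied SAP covers only Groups 4E to 6E, so it does not settle the point for Cohort 2.

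No endpoint definition, analysis set or estimate is shown to change. Severity is minor to moderate.

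**What to change.** - Change footnote 3 so that Visits 04–06 take their windows from the actual date of Visit 03.
- Change footnote 4 so that Visits 07–12 take theirs from the actual date of Visit 06.
- Move the footnote marker on Visit 07 from 3 to 4.
- Make any visit-window check in the electronic data capture system use the same anchors.

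The cost is two footnotes, one marker and possibly one system setting. No visit or procedure is added.

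Separately, the differing statements of the first-booster window in Section 1.2 (Table 4 header and note d), Section 4.1 and Table 11 must be reconciled. The correction above works whichever statement is kept.
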